14.4. Risks and Procedures to Minimize Risk

Potential risks are disclosed to the study patients in the ICF prior to their participation in the study. The risk of the therapeutic intervention is judged comparable in comparison to standard of medical care. The proposed investigations and management strategies are all part of routine optimal care. The identifiable risks are associated with cUTIs. These risks include but are not limited to:

- Allergic reaction to antimicrobial therapy
- Progression or relapse of cUTI
- Nausea, vomiting, headache, skin rash, hypersensitivity reaction, anaphylaxis reaction
- Yeast infection (vaginitis/vulvovaginal candidiasis)
- Progression to acute renal failure

UPH-STD-05-01 Version: 0

Effective Date: 06/23/2023 Page **32** of **44**

- C. difficile infection
- Sepsis

There may be unknown risks.

While there is minimal potential risk of loss of privacy and loss of confidentiality, multiple precautions will be in place to protect the subject's privacy.

15. QUALITY ASSURANCE AND QUALITY CONTROL

15.1. Auditing and Inspecting

The Sponsor, or designee(s), will monitor the study to ensure that the rights and well-being of the subjects are protected, for compliance with the protocol, for compliance with applicable laws and regulations. Quality assurance audits may be performed by the Sponsor or health authority during the course of the study or after its completion.

The PI and sites agree to comply with the Sponsor and regulatory requirements for auditing the study. This includes access to the source documents for source data verification.

15.2. Study Monitoring

Prior to the start of the study, the Sponsor representatives, site personnel, and any third-party vendor representatives will hold at least one meeting to go over the details of the study design and plans for study execution. The delegated study monitor will conduct risk-based monitoring to identify, assess, and mitigate the risks that could affect the quality or safety of a study. Monitoring and data verification may be performed remotely.

15.2.1. Responsibilities of the Investigator(s)

The Investigator must ensure compliance with all procedures required by the study protocol and with all study procedures provided by the Sponsor. The Investigator agrees to provide accurate study data requested by the study protocol (with the help of the CRF or other appropriate documents). If any process includes transfer of data, all protective measures should be in place to protect and maintain patient confidentiality while data is being transferred. The Investigator may appoint other individuals who may be deemed appropriate as Sub-investigators to assist in the conduct of the clinical study. All study staff will be delegated in a timely manner and listed in the TMF. The Investigator will provide all study staff with a copy of the clinical study protocol, ICF, ancillary forms, and all necessary details prior to delegation.

UPH-STD-05-01 Version: 0

Effective Date: 06/23/2023 Page **33** of **44**

15.2.2. Responsibilities of the Sponsor

The Sponsor, or responsible CRO, of this clinical study is responsible for ensuring the proper conduct of the clinical study with regards to ethics, clinical study protocol compliance, and integrity and validity of the data recorded on the CRFs.

15.2.3. Source Document Requirements

The monitoring team will check the CRF/eCRF data against the source documents to verify accurate transfer of data, except for those entries captured directly into the CRF/eCRF as stipulated in the Clinical Trial Monitoring Plan (CTMP).

16. DATA HANDLING AND RECORD KEEPING

All US-based study sites and laboratories providing support for this study, must, where applicable, comply with the Health Insurance Portability and Accountability Act of 1996 (HIPAA). A site that is not a Covered Entity as defined by HIPAA must provide documentation of this fact to the CRO/Sponsor.

An independent, third-party clinical trial management system (CTMS) and/or Electronic Data Capture (EDC) software vendor may be used at the site for laboratory report data and patient-associated document storage. All activities and actions performed on the vendor platform(s) will be tracked and will produce an electronic audit-trail in accordance with regulatory standards.

Paper documents will be used in the event that the CTMS and/or EDC system(s) is not used due to any unforeseen or incidental circumstance causing disruption to data collection. All paper documentation will be subject to ICH-GCP E6(R2) regulations and applicable guidelines.

The PI and/or delegated study staff agree to maintain accurate CRFs and source documentation. Source documents are the originals of any documents that allow verification of the existence of the patient and substantiate the integrity of the data collected during the study.

The CRO and/or Sponsor will supply the site with either paper or electronic CRFs for each patient. CRFs will be completed only by persons delegated by the PI. Corrections will be made so as not to obliterate original data and will be identified and dated by the person who made the correction. The PI/delegates will allow designated representatives and regulatory bodies to have direct access to the source documents to verify the data reported in the CRFs.

UPH-STD-05-01 Version: 0

Effective Date: 06/23/2023 Page **34** of **44**

16.1. Confidentiality

The PI and/or delegated study staff will ensure that the confidentiality of the patient's data will be preserved to the extent permitted by law. All parties will ensure protection of patient personal data and will not include names or other identifiable patient data in any reports, except where required by law. Documents that house patient information, such as signed ICFs and personal information/demographic forms will be maintained and stored by delegated study staff under strict access.

16.2. Source Data and Source Documents

As defined by the International Conference on Harmonization (ICH), source data are defined as all information in original records and certified copies of original records of clinical findings, observations, or other activities in a clinical study necessary for the reconstruction and evaluation of the study.

All source data and source documents will be stored and archived according to local regulatory requirements. For this study, source data and documents include, but are not limited to:

- Signed and dated Informed Consent Form (ICF);
- Name, sex, date of birth and other personal information/demographic information;
- Subject ID;
- Date and time of each visit;
- All clinical measurements and laboratory results;
- Status of patient throughout the study;
- Any first-hand study-related data directly captured on paper and/or entered into eCRFs via tablet, computer or other electronic devices;
- List of concomitant medication;
- Adverse events or changes in health;
- Reason for discontinuation/withdrawal, if applicable.

16.3. Case Report Forms (CRFs)

Case report forms will be created following protocol finalization and approval to capture study data. These forms may be in the form of paper, or may be electronic (eCRFs). An eCRF system, provided by an independent third-party vendor, may be used to capture data. Prior to deployment of the study, the eCRF system will be validated and specified to address source documentation, in accordance with Sponsor and regulatory requirements.

16.4. Data storage and Access

UPH-STD-05-01 Version: 0

Effective Date: 06/23/2023 Page **35** of **44**

Data will be entered into the source documents, checked for discrepancies and queried for any issues in accordance with site-approved SOPs. The sites are responsible for collecting and inputting data into the designated study database, either directly or transcribing from source documents. The database housing the eCRF input will be hosted by the eCRF vendor. All vendor data access and entry can only be performed by authorized users, using a unique user login and password. Login activity and data entry will be tracked in an automated audit trail. The Sponsor, site(s) and CRO will permit study-related monitoring, audits, IRB review, and regulatory inspections, providing direct access to source data/documents. Paper CRFs may also be monitored for completion, queried through internal review by delegated study staff, identified items resolved and documented where applicable, and any required data from source documents will be entered into the final database prior to locking.

16.5. Data Quality Assurance

Data cleaning will be performed to check for completeness and consistency of data using system, programmed, and manual edit checks. Discrepancies in data will be resolved through querying, delegation and resolution in accordance to site SOPs.

UPH-STD-05-01 Version: 0

Effective Date: 06/23/2023

EOS visit? (eradication of the pathogens identified at baseline) Based on provided diagnostic test results (PCR or C&S) 1. Availability of diagnostic results (i.e. acceptable turnaround time to reduce the use of empiric	☐ Emergent infection (new infection or super-infection) ☐ Other (specify:) Score (5) – Excellent (4) – Good (3) – Acceptable
EOS visit? (eradication of the pathogens identified at baseline) Based on provided diagnostic test results (PCR or C&S) 1. Availability of diagnostic results (i.e. acceptable turnaround	☐ Emergent infection (new infection or super-infection) ☐ Other (specify:) Score (5) – Excellent (4) – Good (3) – Acceptable (2) – Needs improvement
EOS visit? (eradication of the pathogens identified at baseline) Based on provided diagnostic test results (PCR or C&S) 1. Availability of diagnostic results (i.e. acceptable turnaround time to reduce the use of empiric broad-spectrum antibiotics)	☐ Emergent infection (new infection or super-infection) ☐ Other (specify:
EOS visit? (eradication of the pathogens identified at baseline) Based on provided diagnostic test results (PCR or C&S) 1. Availability of diagnostic results (i.e. acceptable turnaround time to reduce the use of empiric	☐ Emergent infection (new infection or super-infection) ☐ Other (specify:) Score (5) – Excellent (4) – Good (3) – Acceptable (2) – Needs improvement
EOS visit? (eradication of the pathogens identified at baseline) Based on provided diagnostic test results (PCR or C&S) 1. Availability of diagnostic results (i.e. acceptable turnaround time to reduce the use of empiric broad-spectrum antibiotics) 2. Comprehensibility of	☐ Emergent infection (new infection or super-infection) ☐ Other (specify:
EOS visit? (eradication of the pathogens identified at baseline) Based on provided diagnostic test results (PCR or C&S) 1. Availability of diagnostic results (i.e. acceptable turnaround time to reduce the use of empiric broad-spectrum antibiotics) 2. Comprehensibility of	☐ Emergent infection (new infection or super-infection) ☐ Other (specify:

UPH-STD-05-01 Version: 0

Effective Date: 06/23/2023 Page **38** of **44**

3. Efficiency of diagnostic	(5) – Excellent	
process (i.e. usefulness of the test	(4) – Good	
results in clinical decision	(3) – Acceptable	
making)	(2) – Needs improvement	
	(1) – Unacceptable	
4. Overall satisfaction with the	(5) – Very satisfied	
assigned diagnostic test	(4) – More than satisfied	
	(3) – Satisfied	
	(2) – Partly satisfied	
	(1) – Not at all satisfied	
5. Impact on patient care:	(5) – Strongly agree	
Compared to the comparator test,	(4) – Agree	
clinical decision made with the	(3) – Neither agree nor disagree	
assigned test result has yielded	(2) – Disagree	
better patient clinical outcome	(1) – Strongly disagree	
Total Score:	/2:	5

Score Interpretation:

Weighted summary scores in each criterion range from 1 to 5, with higher scores indicating greater diagnostic and therapeutic value of the specified test. A higher total score indicates better clinical utility of the assigned test than the comparator test.

Total score will be interpreted as follows:

The test method with a total score:

 ≥ 20 = Good clinical utility 10-19 = Moderate clinical utility 0-9 = Poor clinical utility

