8.3. Visit 2 - Treatment (Day 0 + 5)

Visit 2 MUST initiate within 24 hours of the test result (urine C&S or urine PCR as applicable to subject's assigned arm) becoming available and within specified buffer window. Study staff will record the data associated with the PCR test report or C&S test report in a dedicated eCRF, including time of the test reports.

Visit 2 may be conducted virtually, as per treating Investigator's discretion, if the patient care can be continued in an out-patient clinic/setting.

The identity of the patient will be confirmed by verbal verification of DOB and name. The Investigator or delegate will review medical history. Patients will be asked about any changes in their health, and any concomitant treatments administered since the last visit.

UPH-STD-05-01 Version: 0

Effective Date: 06/23/2023

Page 21 of 44

Doc Lab Inc. / Protocol Number 22-UPHUV-01 Advarra IRB Approved Version 0, Date: 12 May 2023 / Pro00071764

The treating Investigator will utilize the results of the patients' randomly assigned study arm for their clinical decision making and patient care. The treating Investigator MUST NOT* review the results of the (unassigned) comparator test before treatment.

*Exception: If the patient's assigned test detects no UTI, the treating Investigator will review the result of the comparator test. In the case of concordant result between two comparators (both negative), the patient will be referred to SOC and excluded from the study. In the case of discordant result, the patient will be referred to SOC and the result of patient care will be followed up by the Investigator or delegate. The patient data will be collected and used for discordant analysis as planned (refer to section 11.3.4).

The treating Investigator shall provide continuous patient care as per their medical decision(s). These include, but are not limited to: request of unscheduled visits, admission/referral of patient to receive in-patient care, administration of IV or oral antibiotics, in/out-patient care, or use of broad-spectrum antibiotics.

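### Appendix I reads a higher satisfaction total as superiority over the comparator test, although at least 15 of its 25 points do not compare the tests

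*Combined protocol and SAP*

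**What the plan says.** Section 11.3.2 lists the Treating Investigator Satisfaction Score, taken from the Appendix I questionnaire at end of study, as a secondary endpoint. The scored block is headed "Based on provided diagnostic test results (PCR or C&S", with the bracket closing after that. Items 1 and 3 ask about the availability of results and their usefulness in decisions. Item 4 begins "4. Overall satisfaction with the" and goes on to name the assigned test. Item 5 opens "Compared to the comparator test" and asks whether decisions made on the assigned test gave a "better patient clinical outcome".

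The Score Interpretation text says "Weighted summary scores in each criterion range from 1 to 5", gives no weights, and then states: "A higher total score indicates better clinical utility of the assigned test than the comparator test". Three bands follow: 20 or more is good utility, and the other two are "10-19 = Moderate clinical utility 0-9 = Poor clinical utility".

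On conduct, section 8.3 says "The treating Investigator will utilize the results of the patients' randomly assigned study arm for their clinical decision making and patient care". Section 8.4 has the investigator complete the form once both test results are available. For analysis, section 11.3.6 provides descriptive and trend statistics for secondary variables and a general alpha of 0.05. It names no between-arm comparison of this score.

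**The concern.** The interpretation sentence turns a sum of mainly absolute ratings into a statement of superiority. A clinician can rate a test highly for speed, usefulness and satisfaction without holding any view on whether the other test would have been better. The one item that does ask for a comparison asks about something the investigator cannot see. The comparator's laboratory result becomes available, but the outcome of treating the same patient on that result does not.

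The rule also makes no use of the randomization. The trial could estimate how satisfaction differs between tests by comparing the two arms. Instead, the only written route from this score to a comparative conclusion is the Appendix I sentence. If the report follows it, high PCR-arm totals could be presented as evidence that PCR has better clinical utility than culture, whatever the totals in the culture arm. The raters are unblinded and record the patient's clinical outcome on the same form.

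**Working it through.** **Inputs (Appendix I).** There are five items, each scored 1 to 5. The maximum total is 25, and the bands are 20 or more, 10–19 and 0–9. No weights are given, so I assume equal weights, which agrees with the maximum.

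**Reproducing the plan's figure.** Maximum = 5 × 5 = 25, as stated. Minimum = 5 × 1 = 5, so totals of 0 to 4 in the lowest band cannot occur.

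**Share of the total that compares the tests.** Item 5 supplies at most 5 of 25 points, or 20%. Items 1, 3 and 4 supply 15 of 25, or 60%, and are absolute. Item 2 (comprehensibility) is cut off in the available text. If it is absolute like its neighbours, as the block heading suggests, the non-comparative share is 20 of 25, or 80%.

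**Can the top band occur without agreement on item 5?** The highest total for a given item 5 answer is 4 × 5 + item 5:

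- item 5 = 1 (strongly disagree): 20 + 1 = 21
- item 5 = 2 (disagree): 20 + 2 = 22
- item 5 = 3 (neutral): 20 + 3 = 23

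All three are in the top band. In the other direction, item 5 = 5 with items 1–4 all at 1 gives 4 + 5 = 9, the lowest band.

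**How many answer patterns behave this way?** There are 5^5 = 3,125 patterns. To reach 20 with item 5 = k, items 1–4 must sum to at least 20 − k, so together they may fall short of their maximum by at most k points. For k = 1 to 4 the number of ways is C(k + 4, 4). For k = 5 it is C(9, 4) − 4, because no single item can lose 5 points.

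| Item 5 | Patterns with total ≥ 20 |
|---|---|
| 1 | 5 |
| 2 | 15 |
| 3 | 35 |
| 4 | 70 |
| 5 | 126 − 4 = 122 |
| All | 247 |

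Of the 247 patterns in the top band:

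- item 5 at 3 or below: 5 + 15 + 35 = 55 (22.3%)
- item 5 at 1 or 2: 5 + 15 = 20 (8.1%)
- item 5 at 1: 5 (2.0%)

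Over all pairs of patterns with unequal totals, the higher total has the lower item 5 answer in 24.1%. These figures count possible patterns and do not forecast real answers.

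**If item 2 were also comparative.** The lowest answer on both item 2 and item 5 would cap the total at 3 × 5 + 1 + 1 = 17, in the middle band. Items 1, 3 and 4 would still contribute 15 points that say nothing about the comparator.

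**Coherence across arms.** Suppose forms in both arms total 21. Applied to the PCR arm, the sentence favours PCR over culture; applied to the culture arm, it favours culture over PCR. Both cannot be true. Only a comparison of the two arms settles the matter, and none is specified for this score.

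**The case against.** The strongest defence is that the sentence is loose wording rather than a decision rule. The bands are introduced by reference to a test method, which suggests that scores are to be read per method; a higher total would then mean higher than the other method's. The form is to be completed with both results in view, and section 8.4 says that it concerns the value of both tests. The endpoint is openly labelled subjective, the study is open-label, and the analysis is descriptive.

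Much of this stands. The per-method reading is possible and would be sensible, but the text does not state it and section 11.3.6 does not plan it. If that is the intent, writing it down is the fix. Having both results in view gives context for item 5. It does not make items 1, 3 and 4 comparative, and there is one total.

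A reader might also infer more than the documents support:

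- *That a total of 21 with item 5 at 1 means the investigator said the comparator was better.* Rejecting a better outcome includes thinking the outcome would have been the same. Utility in this form also covers speed and usefulness, so such a form is not self-contradictory.
- *That reaching 20 is itself a declaration of superiority.* The bands are absolute labels, and the comparative sentence sets no threshold.
- *That this score is the only measure of the decision-making objective.* Table 2 lists objectives and endpoints in blocks without pairing them.

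**Conclusion.** The stated interpretation is wrong as a rule, not merely short of detail. A higher total cannot show that the assigned test is better than the comparator when at least 60% of the points are absolute ratings and the one clearly comparative item concerns an unobserved outcome. Read form by form, it allows each test to be declared better than the other.

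The size is modest. A top-band total without agreement on item 5 is possible (55 of 247 patterns), but how often it would happen cannot be known from the documents. The score is a descriptive secondary endpoint, and neither the primary test nor the sample size depends on it. The conclusion rests on equal item weights and on the readable wording of items 1, 3, 4 and 5. It does not depend on item 2. This is a minor point, worth correcting because it prevents an unsupported superiority statement in the report.

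**What to change.** 1. In Appendix I, remove the reference to the comparator from the sentence that interprets a higher total.
2. In section 11.3.6, base any comparative statement on the difference in scores between the randomized arms, with a confidence interval. An investigator may rate many patients, so the interval should allow for clustering by investigator.
3. Report item 5 separately, labelled as unblinded investigator opinion.
4. Keep the 25-point total and add a sensitivity summary of items 1–4. Replacing the endpoint with a 20-point score and rescaled bands is optional and not needed to cure the defect.
5. Present the bands only as absolute labels. In the same edit, correct the unattainable totals of 0–4 and either state the weights or delete the word weighted.

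The form's items and the data collected do not change. The cost is a documented wording change, completed before the data are analysed and approved under section 13 before it is implemented.

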Appendix II. Urine Sample Collection

- Early morning urine specimens ('first void specimen') are preferred, however routine or random samples are acceptable.
- Upon sample collection, immediately refrigerate the specimen and submit to the central laboratory within 24 hours of collection (maintain at 2-8 °C when transporting).
- If transportation to the central laboratory is expected to exceed 24 hours, whole cups of urine specimen must be frozen. However, for expedited PCR test processing, aliquot 1mL of urine into two* separate 1.5mL Non-Stick RNase-Free microfuge tubes labeled with patient information. Aliquoted tubes (for PCR testing) and the remaining urine specimen in the cup (for C&S testing) must be place in the freezer (< -20°C).

UPH-STD-05-01 Version: 0

Effective Date: 06/23/2023 Page **39** of **44**

*One tube is for immediate processing on the following work day and the other is a backup in case testing needs to be repeated.

Methods	Supplies	Instruction
Clean-	- Sterile 90 mL container	Patient instructions:
catch	- Towelette	Step 1. Wash and dry your hands thoroughly.
Midstream		Step 2. Remove the container lid and set it aside. Do not touch inner surfaces.
		Step 3. Cleanse your urogenital area ("lower parts") with the towelette provided.
		Women: Wipe from front to back between the folds of skin.
		Continue to hold the skin fold apart until the urine sample is
		collected
		Men: Wipe the tip of the penis (if un-circumcised, retract the foreskin).
		Continue to hold the foreskin back until the urine sample is collected
		Step 4. Pass a small amount of urine into the toilet bowl.
		Step 5. Urinate into the container until the container is 1/2 to 2/3 full
		Step 6. Finish urinating into the toilet bowl.
		Step 7. Replace the lid and tighten firmly.
		Step 8. Wash and dry your hands thoroughly.

Note: The collector must NOT combine urine collected from separate voids to create one specimen of sufficient volume, under any circumstances.

Appendix III. Device specification: pathogen targets and Cq ranges, antibiotics resistance genes and Cq ranges

Pathogen targets	Cq ranges for pathogen detection
 Candida albicans, glabrata, parapsilosis, tropicalis 	
Chlamydia trachomatis	Critically High : 10.000 – 21.000
Citrobacter freundii/braakii	High : 22.000 – 26.000
Citrobacter koseri	Medium : 27.000 – 28.000
Enterococcus faecium, faecalis	Low : 29.000 – 32.000
Escherichia coli	Negative : 40.000 – 33.000;
Gardnerella vaginalis	09.000 - 1.000
Klebsiella pneumoniae/oxytoca	
Mycoplasma genitalium	
Neisseria gonorrhoeae	
 Proteus mirabilis, vulgaris 	
Pseudomonas aeruginosa	
Serratia marcescens	
• Staphylococcus (coagulase negative: epidermidis,	
haemolyticus, lugdunensis, saprophyticus)	
Staphylococcus aureus	
Staphylococcus saprophyticus	

UPH-STD-05-01 Version: 0

Effective Date: 06/23/2023 Page **40** of **44**

Streptoccoccus agalactia (group B)	
Streptococcus pyogenes	
Trichomonas vaginalis	
Ureaplasma urealyticum	
Acinetobacter baumannii	
Antibiotic resistance genes	Cq ranges for resistance gene
• Class A β-lactamase; blaKPC	identification
• Class A β-lactamase; CTX-M-Group1	
 Class B metallo-β-lactamase; blaNDM 	Positive : 10.000 – 31.000
Class D oxacillinase OXA-48	Negative : 32.000 – 40.000;
Class D oxacillinase OXA51	1.000 - 9.000
• dfr (A1, A5), sul (1,2) probes (Sulfamethoxazole and	
trimethoprim)	
• ermB, C; mefA	
• IMP, NDM, VIM Groups (Carbapenem)	
MRSA* Mec-A	
• PER-1/VEB-1/GES-1 Groups (ESBL)	
• qnrA1, A2	
• qnrB	
• qnrS	
• tetB, tetM	
• VanA, VanB (Vancomycin)	
ACT, MIR, FOX, ACC Groups (Beta Lactams)	

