9. ASSESSMENTS AND PROCEDURES

9.1. Urine Sample Analysis

Urine samples (at least 8 mL) will be collected from a clean-catch mid-stream urine specimen at V1 and V3. Patients will be instructed to follow the clean catch instructions provided at the collection site. The Investigator or delegate may collect the urine samples using a properly disinfected collection techniques such as through a newly-placed urinary catheter, cystoscopy, or suprapubic aspiration, as per clinical indication (See Appendix II for further procedural guidance). Additional urine sample collection and analysis may be conducted at an unscheduled visit, if deemed necessary by treating Investigator. Specimens must be immediately refrigerated upon collection and submitted to the central laboratory within 24 hours of collection. Specimen must be stored and maintained at 2-8 °C when transporting. If transportation to the central laboratory is expected to exceed 24 hours, whole cups of urine specimen must be frozen.

Obtained urine samples will be labelled with subject ID, DOB, visit number, study ID, method of collection, date and time of collection. The collected sample will be placed in a small bag along with the test requisition form. The processing laboratory will aliquot the sample upon receipt, one to be analyzed by PCR (maximum 3mL) and the other to be analyzed by C&S (minimum 5mL). The sample will be stored under the appropriate temperature conditions until analysis of the sample.

Urine C&S

All urine samples for Urine C&S will be shipped to the central laboratory. Urine culture, isolation of uropathogen(s), initial identification of pathogen(s) and bacterial counts in urine will be conducted in the central laboratory.

Urine samples will be cultured and quantified using a calibrated loop to identify a quantitative count of bacteria at a lower limit of 10⁵ CFU/mL. All purified pathogen(s) will be further analyzed for species identification and antimicrobial susceptibility. The analysis results will be recorded in the source document and eCRF.

Urine PCR

Urine samples will be analyzed using the listed molecular testing devices:

• KingFisher Duo Prime

UPH-STD-05-01 Version: 0

Effective Date: 06/23/2023 Page 23 of 44

Doc Lab Inc. / Protocol Number 22-UPHUV-01 Advarra IRB Approved Version 0, Date: 12 May 2023 / Pro00071764

- QuantStudio 6 and 7 Flex Real-Time PCR System
- QuantStudio 12k Flex Real-Time PCR System

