11.3.4. Discordant Analysis on the Results of Molecular versus Conventional Methods

The level of discordance between the molecular method and the conventional method will be assessed by calculating the global study positive percent agreement (PPA) and negative percent agreement (NPA) from the results of the cUTI tests. It is noted that evaluating and incorporating the conventional method's inherent performance characteristics is out of scope for this study; hence, the NPA/PPA metrics serve only as estimates into the sensitivity and specificity of the molecular method.

The PCR and the C&S results will be captured and summarized using the following matrix:

	C&		
PCR	Positive	Negative	Total
Positive	a	b	С
			(a+b)
Negative	С	d	D
			(c+d)
Total	A	В	Е
	(a+c)	(b+d)	(a+b+c+d)

where each value a, b, c and d is a total number of pair-results collected in the study. The NPA/PPA metrics are calculated as:

$$PPA = \frac{a}{A} \times 100\%$$

$$NPA = \frac{d}{B} \times 100\%$$

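### Urine for culture is frozen when transport exceeds 24 hours, with no validated recovery, no flag and no separate analysis, so true culture-positives can be reported as negative

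*Combined protocol and SAP*

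**What the plan says.** The default in Section 9.1 and Appendix II is refrigeration at 2-8 °C and delivery to the central laboratory within 24 hours. The exception is the issue. Section 9.1: "If transportation to the central laboratory is expected to exceed 24 hours, whole cups of urine specimen must be frozen". Appendix II says that "the remaining urine specimen in the cup (for C&S testing) must be place in the freezer", at a temperature below -20 °C.

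In the same exception Appendix II treats PCR differently: "for expedited PCR test processing, aliquot 1mL of urine into two* separate 1.5mL Non-Stick RNase-Free microfuge tubes". Its footnote adds: "One tube is for immediate processing on the following work day". Yet the sentence that freezes the cup also sends these tubes to the freezer.

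Section 9.1 ships every culture sample to the central laboratory and reads it with "a calibrated loop to identify a quantitative count of bacteria at a lower limit of 10⁵ CFU/mL". No other limit applies to thawed urine. Neither document section describes validated recovery, a frozen-specimen field, a not-evaluable category or a sensitivity analysis.

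The culture result is used in four places:

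- **Section 8.3:** it guides care in the C&S arm. If the assigned test is negative, the investigator sees the other result. Patients negative on both are excluded; discordant patients go to standard of care and are followed.
- **Section 11.2:** a positive PCR or C&S result admits a patient to Mod-ITT.
- **Section 11.3.4:** culture is the reference for PPA and NPA, and "the NPA/PPA metrics serve only as estimates into the sensitivity and specificity of the molecular method".
- **Section 11.3.2:** eradication needs culture below 10^5 CFU/mL and PCR non-detection, and turnaround runs from collection.

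**The concern.** A CFU count needs organisms that still grow; PCR amplifies target sequences. A handling rule that reduces viability therefore acts on one method and not, or less, on the other. With a fixed reporting limit, a specimen that was above 10^5 CFU/mL at collection can be below it after thawing and is then reported as negative.

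In this trial the comparator result is also the intervention in one arm. A false negative there removes the information the arm is meant to test, opens the PCR result to the investigator and moves the patient to standard of care. On the reading of Section 11.2 that either positive test suffices, the patient still counts in the C&S arm of Mod-ITT if PCR is positive. If PCR missed the infection, a lost culture makes the pair a concordant negative and the patient is excluded, in either arm. None of this can be separated afterwards if frozen status is not recorded.

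**Working it through.** **Check against the plan's own figure.** The documents give no figure for freezing. The only related one is the sample size. Full enumeration of the one-tailed Fisher test with 287 per arm, 0.7 against 0.8, alpha 0.05, gives power 0.8513193, and rejection probability 0.04044 when both rates are 0.8. Both match Section 11.1, so the same routine is used in step 3.

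**1. Agreement table.** Assumed pairs per 100: a = 50 (both positive), b = 20 (PCR only), c = 3 (culture only), d = 27 (both negative). Let z be the share frozen and l the share of frozen culture-positives that fall below the limit; L = z × l. PCR is assumed unchanged and the loss independent of the PCR result. Then a' = a(1-L), b' = b + aL, c' = c(1-L), d' = d + cL.

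| z, l | L | a' | b' | c' | d' | NPA = d'/(b'+d') | PPA = a'/(a'+c') | Overall |
|---|---|---|---|---|---|---|---|---|
| none | 0 | 50 | 20 | 3 | 27 | 27/47 = 57.4% | 50/53 = 94.3% | 77.0% |
| 0.1, 0.2 | 0.02 | 49 | 21 | 2.94 | 27.06 | 27.06/48.06 = 56.3% | 49/51.94 = 94.3% | 76.1% |
| 0.5, 0.5 | 0.25 | 37.5 | 32.5 | 2.25 | 27.75 | 27.75/60.25 = 46.1% | 37.5/39.75 = 94.3% | 65.3% |

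The culture-positives lost are 53 × L = 1.1 and 13.3 per 100. PPA does not move because (1-L) cancels; if losses fell mainly on pairs that PCR misses, it would rise.

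A second assumed setting gives the same pattern: 720 patients, 40% or 60% culture-positive, PPA 90%. At L = 5%, NPA falls from 70.0% to 68.1% or 65.8%, and from 90.0% to 87.4% or 84.4%. At L = 25% it falls to 61.4% or 53.6%, and to 78.6% or 68.2%.

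**2. Exclusions and Mod-ITT.** Pairs moving from c to d number 3 × L = 0.06 to 0.75 per 100; these are PCR misses that become concordant negatives. Pairs moving from a to b stay in Mod-ITT. As a share of Mod-ITT they are 1/(100 - 27.06) = 1.4% to 12.5/(100 - 27.75) = 17.3%.

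**3. Primary endpoint, one adverse scenario.** Assume a true favorable rate of 75% in both arms, with the rate in affected C&S-arm patients lower by 10 to 30 points. The spurious difference is affected share × drop.

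| Affected share of C&S arm | Spurious difference | One-sided rejection rate |
|---|---|---|
| 0 | 0 | 4.1% |
| 2.5% | 0.25 to 0.75 points | 4.8% to 6.3% |
| 10% | 1.0 to 3.0 points | 7.2% to 17.8% |
| 25% | 2.5 to 7.5 points | 14.5% to 60.0% |

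The last row exceeds the 17.3% from step 2 and is extreme.

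**4. Eradication.** Assume end-of-study culture-positive 10% to 20%, PCR-positive 20% of culture-negatives, PCR detecting 90% to 100% of culture-positives, and L = 5% to 25%. The composite rises by (culture-positive share) × L × (1 - detection): at most 0.20 × 0.25 × 0.10 = 0.5 points, at least 0, and alike in both arms.

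**5. Turnaround.** Section 3 puts culture at 48 hours or more. If that excludes transport, culture in this branch takes over 24 + 48 = 72 hours from collection. One PCR tube is meant for the next work day.

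**The case against.** The rule is a contingency. If transport over 24 hours is rare, the effect is trivial; the low case above moves NPA by 1.1 points. The documents state neither that freezing kills uropathogens nor that PCR is spared. Both points stand: the text of the rule is certain, the size is not.

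A reader might infer that freezing shifts agreement in PCR's favor. The plan does not support that. Section 11.3.4 uses NPA and PPA to gauge PCR, so lost cultures lower NPA and overall agreement and make PCR look less specific. Only an informal reading of the extra PCR-only pairs as superior PCR sensitivity would favor PCR.

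A reader might also infer that easier eradication helps the PCR arm. Both tests are run on every patient and PCR non-detection is required as well, so there is no direct arm advantage.

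On the primary endpoint, Section 8.3 mitigates: a negative culture opens the PCR result and the patient is referred to standard of care. That limits harm to the C&S-arm rate. It also brings PCR information into the C&S arm, which could dilute a true difference, so the direction of bias is not fixed.

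Counting transport in turnaround is defensible in a utility study, because the clinician waits through it. What remains is the unequal handling in this branch, which has nothing to do with viability.

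**Conclusion.** The point holds as a weakness in comparator handling that should be corrected. A stated rule freezes the culture portion, the reading limit is fixed, and nothing identifies or separates the specimens concerned. If viable counts fall and PCR detection is largely intact, C&S-guided care, exclusions, NPA and overall agreement then reflect handling rather than assay performance.

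Under the assumed inputs NPA falls by 1.1 to 11.3 points (57.4% to 56.3% or 46.1%) with PPA about unchanged. Eradication moves by 0.0 to 0.5 points. The primary contrast can be distorted, by an amount and in a direction that the documents do not settle. Turnaround in this branch can favor PCR through its expedited tubes. The stronger conclusion, that agreement and eradication are tilted toward PCR, does not follow.

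**What to change.** - **Section 9.1 and Appendix II:** do not freeze the culture portion unless recovery at the 10^5 CFU/mL limit has been validated.
- **eCRF:** add frozen yes/no and laboratory receipt time.
- **Classification:** call an unvalidated frozen or late culture not evaluable rather than negative. State how such patients are handled in Mod-ITT and under Section 8.3, which now covers only a negative assigned test.
- **Analysis:** leave frozen cultures out of PPA/NPA and out of the culture part of eradication, with a stated missing-data rule for the latter. Add a primary-endpoint sensitivity analysis that omits, in both arms, patients whose baseline culture was frozen.
- **Turnaround:** report receipt-to-result time beside the defined collection-to-result time.
- **Appendix II:** reconcile the sentence that freezes both PCR tubes with the footnote on next-work-day processing.

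The cost is wording in two sections, two data fields, SAP text and, if freezing is kept, a recovery validation. The downside is that some late specimens will yield no evaluable culture.
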